4. OBJECTIVES

4.1. General objective:

To develop and determine the efficacy of a dietary intervention that promotes the elimination of SFA consumption from red and processed meats and to evaluate its impact on lipid and cardiovascular risk markers in patients with dyslipidaemia.

4.2. Specific objectives:

- a. To develop the necessary elements for the application of a dietary intervention that promotes the reduction of the consumption of SFA from red and processed meats in patients with dyslipidaemia
- b. To test the efficacy of a dietary approach aimed at avoiding red and processed meat, in the context of a Mediterranean dietary pattern, on LDL-C and palmitic acid (main results) after eight weeks of intervention, compared to the usual approach of healthier lifestyle recommendations.
- c. To determine the metabolic alterations parallel to the changes in SFA intake, from red and processed meat, by means of a complete lipid and metabolomic profile, as well as the determination of other intermediate markers of CVD.
- d. To assess the effect of the intervention on dietary intake and other lifestyle factors.
- e. To evaluate the effect of the intervention on the composition of the gut microbiota and its derived plasma metabolites that could be influenced given the expected metabolic benefits;
- f. Establish a working panel with patient and public participation (PPP) as well as health professionals, to improve research management and dissemination of project results.

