5.6. Definition of variables: main and secondary results

With the determinations and measurements derived from the CADIMED study, it is proposed to investigate the following results (comparing the intervention group and the control group):

- 1) Main results: changes in LDL-C and fatty acid profile in erythrocytes after 8 weeks of intervention
- 2) Secondary outcomes:
 - a. Changes in other metabolites derived from lipid and metabolomic profile analysis, including circulating fatty acids, HDL-C, total cholesterol, triglycerides, and endogenous and exogenous metabolites related to cardiovascular risk and meat consumption (e.g., TMAO, etc.);
 - b. Changes in other related markers of cardiovascular risk, including biomarkers of inflammation and endothelial damage, insulin resistance, and diabetes (glucose, insulin, HbA1c, C-reactive protein, IL6, TNF-alpha), blood pressure, weight, and body and waist mass index;

- c. Changes in the gut microbiota and derived metabolites
- d. Changes in dietary intake (measured by 24-h recall): SFA intake, total energy intake, total fat, sugar, fiber, salt, general dietary patterns, red and processed meat consumption.
- e. Changes in other lifestyle-related factors: collected through physical activity, smoking, and alcohol questionnaires

3) **Evaluation of the process**: analyses of both quantitative and qualitative measures will be included to understand whether the intervention has worked and through which processes. These measures include: the rate of recruitment of volunteers and the rate of patients completing the study; acceptance of the intervention through questionnaires at the end of follow-up; the use of the mobile application to carry out changes in the diet as well as the self-monitoring of intake; measures that evidence the contamination of the control group; changes in patients' ability and knowledge about diet, SFA, and cardiovascular disease.

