5.7. Data analysis

Sample size

A recent randomized, controlled, peer-to-population trial testing similar dietary approaches to reduce SFA intake showed a long-term change in LDL-C of approximately 15 mg/dL (SD26).¹⁹ If 78 participants are recruited in each group ($n = 156$), it is expected to detect a minimum difference of 15 mg/dl between the intervention group and the control, with a power or detection capacity of 90%, an error $\alpha = 0.05$ and a dropout rate of 20% using intention-to-treat analysis, so the final sample size includes an additional 20% of participants to mitigate dropouts.

Statistical analysis of primary and secondary outcomes

Baseline characteristics will be summarized in descriptive statistics in each study group, statistical analysis will be performed with STATA IC 16.0 software (College Station, TX: StataCorp LLC 2019). Descriptive statistics will be presented with standard deviation (SD) and 95% confidence intervals. Continuous variables will be presented as mean and standard deviation unless the use of the median and interquartile range is necessary; Categorical variables will be expressed as frequencies and percentages.

Efficacy results will be analysed by intent to treat, i.e., all participants will be assessed according to the group to which they are randomly assigned, regardless of their adherence. The analysis of effectiveness measures will use data from all participants for whom a baseline and monitoring measure exists. A linear regression model will be used to calculate the difference in measures with 95% confidence intervals, with adjustment of the initial values of the dependent variable and the place of recruitment. Before the analysis, the assumptions of linear regression, specifically homoscedasticity and the normality of the residual distribution, will be explored. Where these assumptions are not met, appropriate non-parametric analyses shall be used. The sensitivity of the results to confounders due to

differences in baseline characteristics will also be examined. A second sensitivity analysis will use the techniques of "baseline observation carried forwards" (using the initial measure of the variable) and "multiple imputation" (using information about the assigned group and the characteristics of the participants) to impute missing values in the variables of the main outcome. An exploratory analysis of subgroups of results will be carried out according to sociodemographic characteristics.

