5.8.1. Lipid metabolism, endothelial function and inflammatory markers

Fasting venipuncture blood samples will be obtained at the beginning and end of follow-up: two 10 mL tubes of K2E EDTA, and two 10 mL tubes of serum separator gel. First, part of the sample will be processed in the hospital according to its own established protocols to obtain blood biochemistries for the blood lipid fractions: total cholesterol, LDL-C (primary outcome), HDL-C, non-HDLC, triglycerides, glucose, insulin, HbA1c and CRP.

The rest of the samples will be processed at INYTA to obtain plasma and stored (-80 °C) until they are processed for analysis. The new LC-MS will be used to determine a specific plasma fatty acid profile, including palmitic acid (primary outcome), among others. Other plasma biomarkers of endothelial function, such as ICAM-1, VCAM-1, ELAM-1, and MPO, will be determined using Luminex®'s xMAP technology and MULTIPLEX kits; as well as endothelin-1 and angiotensin II using ELISA kits. Inflammatory biomarkers in plasma will also be determined with Luminex® xMAP and HSTCMAG-28SK kits, including IL-6, IL-8/CXCL8, IL-10, IL-23, TNF- α , IFN- γ . ELISA kits will be used to quantify lipopolysaccharides (LPS) and LPS-binding lipoprotein (LBP).

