5.8.4. Statistical analysis of metabolomic and metagenomic data

A "Knowledge Discovery from Databases" (DCBD) process will be followed, which will consist of:

- Selection of variables of interest and groups of subjects for analysis.
- Identify distinct clinical feature sets that are grouped into particular individual groups (phenotypic sets) without regard to their microbiota/metabolomic background.
- Examine the response associated with the intervention in each individual identified phenotypic set.

- Identify metabolomic networks composed of DMRs and metabolites that interact with each other.
- Integration of all previously identified patterns into a multi-layered space using genetic algorithms. The idea of this final step is, once the interesting variables derived from each of the previous approaches (phenotype, microbiota and metabolomics) have been identified, to incorporate them all together for the construction of a predictive model that allows the classification of good and bad responders to treatment.

To this end, different statistical methodologies will be used to identify anomalies, groups or patterns of metabolites, including principal component analysis (PCA) for the initial clustering. To differentiate metabolite patterns between the intervention and control groups, before and after the intervention, a novel multivariate approach, orthogonal partial least squares multiblock analysis of variance (AMOPLS), will be used. The AMOPLS consists of the application of a core-based multiblock OPLS approach on the pure matrices and those augmented by the residues arising from the ANOVA decomposition of the design response matrix and provides, as a product, a global view of the important effects on the model, which allows its interpretation. Analysis of variance and/or linear regression will test the main effects of: 1) time (follow-up vs. baseline); 2) intervention group vs. control; 3) interaction time x intervention group. Univariate analyses will be used to compare baseline means between the intervention and control groups using Student's t-tests. A false discovery rate (q) will be calculated to reduce false positives with a cut-off point < 0.1.

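### Two main results are named, but sample size, alpha and power are set for LDL-C alone, and nothing says how the fatty-acid result counts

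*Protocol*

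**What the plan says.** The protocol gives two outcomes equal rank but describes the second in different ways:

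- Section 5.6: "Main results: changes in LDL-C and fatty acid profile in erythrocytes after 8 weeks of intervention". The same section lists circulating fatty acids among the secondary outcomes.
- Section 4.2, objective b: efficacy is judged "on LDL-C and palmitic acid (main results) after eight weeks of intervention". The Summary names the same pair as the main objective.
- Section 5.8.1 labels LDL-C a primary outcome and, separately, describes a "specific plasma fatty acid profile, including palmitic acid (primary outcome), among others".

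The sample size paragraph in section 5.7 deals with one outcome. Its planning input is a previous trial that "showed a long-term change in LDL-C of approximately 15 mg/dL (SD26" mg/dL). For 78 per group the aim reads: "it is expected to detect a minimum difference of 15 mg/dl between the intervention group and the control". The stated power for this is 90%. One alpha is given, next to the dropout percentage: "an error $\alpha = 0.05$ and a dropout rate of 20". No effect size, SD or power appears for any fatty acid.

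The analysis paragraph of section 5.7 applies one linear regression with 95% confidence intervals to the efficacy measures. It gives no order of testing, no split of alpha, and no statement that one or both main results must succeed. The only control of false positives is in section 5.8.4, for metabolomic and metagenomic data: "A false discovery rate (q) will be calculated to reduce false positives with a cut-off point < 0.1".

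**The concern.** Alpha and power describe a decision. Section 5.7 states them as if the decision rested on LDL-C, while sections 4.2, 5.6 and 5.8.1 rest it on LDL-C and a fatty-acid result. Followed as written, a trial with no LDL-C difference could still report a positive main result through a fatty acid, at a false-positive risk above the stated 5%. If instead both results are required, the chance of success is not the stated 90%. The uncertain definition of the second result (erythrocyte or plasma, one acid or a profile) adds room to choose after the data are seen.

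**Working it through.** **Inputs from section 5.7:** difference 15 mg/dL, SD 26 mg/dL, alpha 0.05, power 90%, 20% added for dropout, 78 per group. Allocation is 1:1 (section 5.4). Sidedness is not stated; two-sided is used here because one-sided needs only 52 evaluable per arm and does not lead to 78.

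**Step 1. Reproduce the stated sample size.** Evaluable per arm = 2 x (z0.975 + z0.90)² x SD² / difference² = 2 x (1.960 + 1.282)² x 676 / 225 = 63.1, rounded up to 64, or 65 with the t distribution. Adding 20%: 65 x 1.2 = 78. The figure is reproduced as a calculation for LDL-C alone at the full alpha.

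After 20% loss, 78 x 0.8 = 62.4 remain per arm. With 62, the standard error is 26 x √(2/62) = 4.67, and power = Φ(15/4.67 − 1.960) = Φ(1.25) = 89.5%. The 90% statement is sound for LDL-C.

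**Step 2. Success on either result, one fatty acid, each at two-sided 0.05.** If neither outcome truly differs and the tests are independent, the family-wise error is 1 − 0.95² = 9.75%. From the bivariate normal, with assumed correlations between the test statistics:

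| Correlation | Family-wise error |
|---|---|
| 0 | 9.75% |
| 0.3 | 9.5% |
| 0.5 | 9.1% |
| 0.8 | 7.8% |

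The upper bound is 10%. If the profile in section 5.6 means several fatty acids, each able to count, the error is higher. Its size depends on the number of acids, which the protocol does not give.

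**Step 3. Success on both results, each at 0.05.** Alpha is kept. Joint power cannot exceed the power for LDL-C, and its value is unknown because the protocol has no planning figures for the fatty acid. As an illustration only, take 90% for LDL-C:

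| Assumed power, fatty acid | Joint, correlation 0 | Joint, correlation 0.5 |
|---|---|---|
| 50% | 45% | 48% |
| 80% | 72% | 75% |
| 90% | 81% | 83% |

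**Step 4. Equal split, 0.025 each.** With 62 per arm, LDL-C power = Φ(3.21 − 2.241) = 83%. Restoring 90% needs 75 evaluable per arm, so 75 x 1.2 = 90 or 75 / 0.8 = 94 recruited per arm: 180 to 188 in total instead of 156.

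**Step 5. Fixed order, LDL-C first at 0.05, fatty acid second only if LDL-C is significant.** The family-wise error stays at 5%, and LDL-C keeps its 89.5% power with 156 recruited. Power for the second result remains unknown.

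**The case against.** The strongest reply is that no stated number is wrong. Section 5.7 ties alpha 0.05 and 90% power to a 15 mg/dL difference in LDL-C, and Step 1 confirms them. A rule for combining two main results is commonly left to the statistical analysis plan, which may exist and is not shown. The protocol nowhere says that success on either result is enough; the objectives join the two with *and*. A 5% test for each outcome is inferred from the 95% intervals and the single alpha.

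Much of this stands, and it rules out three stronger readings.

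- A reader might infer that either the stated alpha or the stated power must be false. That does not follow: a fixed order with LDL-C first (Step 5), or LDL-C as sole primary outcome, keeps both.
- A reader might put the error at 43% to 80%, from 1 − 0.95^(k+1) with 10 to 30 fatty acids plus LDL-C. The protocol gives no such count, and the Summary and sections 4.2 and 5.8.1 name a single acid.
- A reader might quote a definite joint power. Any such value rests on a fatty-acid power that the protocol does not supply.

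What the reply does not remove is the mismatch inside the protocol. It gives two outcomes equal rank, plans for one, and defines the other inconsistently. A testing rule in a separate plan would still leave sections 4.2, 5.6, 5.7 and 5.8.1 to be brought into line with it.

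**Conclusion.** The point holds in a limited form. Sample size, alpha and power are correct for LDL-C and apply to LDL-C only; they do not describe a claim on the main results together. Under an either-result reading with one fatty acid the error is about 9 to 10%, assuming a 5% test for each outcome and correlation of no more than 0.5. It is higher, by an amount that cannot be fixed from the protocol, if the whole profile counts. Under a both-results reading alpha holds, but joint power is capped by the LDL-C figure and otherwise unknown. This should be fixed because the remedy is cheap and closes a route to a positive main claim when LDL-C shows nothing. It is not a fatal flaw, since the planned numbers support the LDL-C question.

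**What to change.** Amend sections 5.6 and 5.7 before any outcome data are analysed:

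1. Test LDL-C first, at two-sided 0.05.
2. Name one palmitic acid measure in one matrix, and test it at 0.05 only if LDL-C is significant. Make the Summary and sections 4.2, 5.6 and 5.8.1 agree on that measure.
3. Make all other fatty acids secondary.
4. State that the 90% power refers to LDL-C only.

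The cost is a few sentences. Recruitment, visits and LDL-C power are unchanged. The price is that palmitic acid cannot be claimed as a main result if LDL-C fails. If the team does not accept that, the alternatives are an alpha split with about 180 to 188 participants, or a both-required rule backed by a power calculation for the fatty-acid outcome.

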6. USEFULNESS AND APPLICABILITY

Patients at risk of cardiovascular disease will benefit the most from the results of this project. Clinical guidelines for reducing cardiovascular risk emphasize the importance of dietary change and recommend that all patients with dyslipidaemia be supported to change their diet. However, dietary interventions are uncommon and there is limited evidence of their effectiveness in the setting of routine primary or secondary care. At present, there are no comprehensive resources to enable physicians and health care professionals to offer brief dietary advice on the management of dyslipidaemia. This project will develop and test a dietary intervention that is easy to implement by clinical staff without much prior knowledge, but also intuitive so that patients with elevated LDL cholesterol can follow and maintain a healthier diet. If we get the expected results, this project will provide an effective approach to offer dietary advice within the Spanish healthcare system. The low cost and increased scalability of this intervention could substantially help the Spanish healthcare system to manage the large number of patients at risk of CVD who could benefit from this intervention. This in turn could translate into lower costs derived from medical care in the Spanish population.

In addition, the results of this project will inform food-based dietary guidelines on the most promising approach to the treatment of dyslipidaemia at the population level. Therefore, the findings of this study will be relevant to other countries where red and processed meat intake is above dietary recommendations, e.g. the UK or the US. The intervention materials and mobile app that will be developed in this project (potential intellectual property) will provide a low-cost, widely disseminated approach to providing dietary advice to all people who need it.

Finally, if a reduction in red and processed meat leads to health benefits, this will also have implications for global warming and environmental sustainability, as consuming less red meat could help protect the environment as well as improve human health. Therefore, this project will also contribute to achieving the Sustainable Development Goals (Sustainable Development Goals) by promoting healthy eating habits that are compatible with human and planetary health.

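### Acceptance is asked only at the end of follow-up, so the planned 20% of dropouts have no planned opportunity to answer and the result would come mainly from completers

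*Protocol*

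**What the plan says.** Section 5.6 of the protocol describes a process evaluation with quantitative and qualitative measures, meant to show whether and how the intervention worked. One of these measures is "acceptance of the intervention through questionnaires at the end of follow-up". The same list contains "the rate of recruitment of volunteers and the rate of patients completing the study" and "the use of the mobile application to carry out changes in the diet as well as the self-monitoring of intake".

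Table 1 in section 5.3 shows one visit after the allocation visit, the end visit. It has no row for an acceptance questionnaire, and no questionnaire at withdrawal is described anywhere.

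The sample size paragraph of section 5.7 plans for "a dropout rate of 20% using intention-to-treat analysis". The imputation methods in that section are limited to the main outcome variables.

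Section 6 gives the intended use: "The low cost and increased scalability of this intervention could substantially help the Spanish healthcare system".

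**The concern.** Acceptance and dropout are probably related. A patient who dislikes an app-supported diet without red or processed meat has more reason to leave than one who likes it. If views are collected only from those still present at the end, the people most informative about poor acceptance are the likeliest to be absent.

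The claim of a low-cost, scalable approach in section 6 concerns everyone who would be offered the intervention, so acceptance among those who finished answers a narrower question. If dropout differed between the arms, a comparison of acceptance between them would also be open to selection.

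The timing matters more than the later analysis. A denominator can be settled in an analysis plan, but no analysis plan can recover answers that were never requested.

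**Working it through.** **Inputs from the protocol (section 5.7).** 78 patients per arm ("If 78 participants are recruited in each group"), dropout 20%, LDL-C difference 15 mg/dL, SD 26, power 90%, α 0.05 (sidedness not stated; two-sided assumed).

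**Not given in the protocol.** Any acceptance level, threshold or denominator, or how dropouts' views compare with completers' views. These are varied below.

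**Step 1: the protocol's own figure.** The normal approximation gives n = 2 × [26 × (1.96 + 1.28)/15]² ≈ 63.1, so 64 per arm. The t-based n is 64.1, so 65. Adding 20% gives 65 × 1.2 = 78, the stated number. The 20% dropout is therefore the protocol's working assumption, and it implies 78 × 0.20 = 15.6, about 16 early leavers per arm.

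**Step 2: formula.** Let a be acceptance among completers, d the dropout proportion, and f the dropouts' acceptance as a fraction of a. Assume that all completers answer.

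- Acceptance among all randomised = a(1 − d) + f·a·d
- Gap between completers and all randomised = a·d·(1 − f)

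**Step 3: results with d = 0.20.**

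| a (completers) | All randomised, f = 0 | Gap, f = 0 | Gap, f = 0.5 | Gap, f = 1 |
|---|---|---|---|---|
| 50% | 40% | 10 points | 5 | 0 |
| 70% | 56% | 14 points | 7 | 0 |
| 80% | 64% | 16 points | 8 | 0 |
| 90% | 72% | 18 points | 9 | 0 |
| 100% | 80% | 20 points | 10 | 0 |

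Example: a = 80%, f = 0 gives 0.80 × 0.80 = 64%, a gap of 0.80 × 0.20 = 16 points.

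**Step 4: what the 20% alone fixes.** If dropouts accept no more than completers, the gap lies between 0 (f = 1) and 20 points (a = 100%, f = 0). Counting whole patients changes little: with 62 completers of 78, the gaps at f = 0 for a = 70%, 90% and 100% are 14.4, 18.5 and 20.5 points.

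**Step 5: direction.** Nothing in the arithmetic forces the gap to be positive. With a = 80% and every dropout accepting, the all-randomised figure is 0.64 + 0.20 = 84%, above the completers' 80%. The expectation of a lower figure rests on the plausible link between dislike and dropout, not on data in the protocol.

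**The case against.** The strongest reply is that the protocol defines no acceptance rate. It names a questionnaire among mixed quantitative and qualitative measures, and the denominator and handling of non-response for a descriptive measure are commonly left to the analysis plan. That is right, and a missing denominator is not the point made here. What stands is the timing of collection, which the protocol itself sets.

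Second, the completion rate and app use are in the same list, so early leavers do not vanish from the process evaluation. This also stands in part. But multiplying completion by completers' acceptance gives only the f = 0 bound, and app use records behaviour, not opinion.

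Third, a reader might infer that dropouts can never be asked. The documents do not say so. Table 1 does not tie the questionnaire to attendance at the end visit, and section 5.7 keeps participants in the analysis whatever their adherence, so someone who abandons the diet may still be followed and may still answer. The supported statement is that those who leave follow-up early have no planned opportunity.

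Fourth, section 6 does not mention acceptance, and no decision threshold depends on it. That limits the weight of the point.

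**Conclusion.** The point holds as a minor weakness in data collection. Acceptance would come mainly from completers. If dropouts accept less, the figure for all randomised patients would be 0 to 20 points lower, given the planned 20% dropout and full response among completers.

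A reader might take 14 to 18 points as the expected overstatement or as its ceiling. It is neither. It requires 70 to 90% acceptance among completers, which the protocol does not state, and rejection by every dropout. With dropouts at half the completers' rate the range is 7 to 9 points, and with equal acceptance it is zero. A reader might also conclude that upward bias is established; it is plausible but not shown.

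The effect is confined to one descriptive process measure. The LDL-C and fatty-acid analyses are not touched.

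**What to change.** In section 5.6, change the timing of the acceptance questionnaire to: *at the end of follow-up or, for those who leave early, at withdrawal through the study app or by telephone*. Both channels already exist in the study, since pre-selection is by telephone and both arms use the app.

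Report acceptance among responders together with the completion rate. Give the all-randomised figure, with non-responders counted as not accepting, only as a lower bound. As a headline it would treat every loss, including illness or relocation, as rejection.

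The cost is a wording change and one short contact for about 16 patients per arm. Some will not respond, so the gap is narrowed rather than closed, and the reported acceptance may be less favourable.
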